Workshops and meetings will be held to inform the physiotherapists participating in the project. Before starting recruitment, one full day workshop on falls prevention and OEP is held for all therapists. Following start-up of recruitment and until the end of the project one workshop will be held approximately every fourth months. These last half a day and include one lecture on a topic concerning older people and time for discussion on the development of the project. Additional to the workshops, the researcher will have monthly meetings with the physiotherapists in the different municipalities. In order to make sure that the intervention is performed as intended, a fidelity checklist based on the OEP-manual has been developed. The physiotherapists use the checklist when conducting the home visits and phone calls.

Outcome measures

Following recruitment participants are assessed before they are randomised. Assessors are blinded to the participants' group assignment. The time window between baseline assessment and start of intervention is aimed to be within two weeks, and the same time window for assessments due at three and six months. Measurements and their order are selected to avoid physical and mental fatigue of the participants. Outcome measures that are employed have established reliability and validity, as recommended by the CONSORT group [50]. In addition to improving measurement quality and outcomes, it enables direct comparisons with other studies that investigate HRQOL and can possibly contribute to meta-analyses.

At baseline the Mini Mental State Examination (MMSE), a measurement of "Global cognitive function", is performed and is used as exclusion criteria. The maximum score is 30. A score below 23 indicates cognitive impairment and these participants are excluded [51]. Sociodemographic characteristics, like age and education, are also assessed at baseline. Primary and secondary outcome measures will be performed at baseline, at three months and at six months' follow-up.

Primary outcome variable

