HRQOL is the primary outcome measured by the Short Form 36 Health Survey (SF-36) [52]. This is a generic and validated questionnaire which, translated into Norwegian, is conducted as an interview [53]. The 36 items in SF-36 are grouped into eight health status scales: physical functioning, role limitations due to physical problems and due to emotional problems, bodily pain, general health perception, vitality, social functioning and mental health [52].

Secondary outcome variables

In addition to the SF36, the EQ-5D (1990 EuroQOL EQ-5D) is reported. The EQ-5D is a generic and validated questionnaire [54-57]. It describes five dimensions of HRQOL (mobility, self-care, usual activities, pain/discomfort, anxiety/depression), each of which can take one of five responses at five levels of severity (no problems/slight problems/moderate problems/severe problems/severe problems/extreme problems).

Physical function includes measures of balance, gait speed, muscle strength as well as activities of daily living. The Bergs Balance Scale is a 14-item scale, which is applied to assess static and dynamic balance in older adults [58]. Gait speed is assessed by measuring usual walking speed over four meters [59] and muscle strength is measured by the 30 seconds sit to stand test [60]. Instrumental ADL is recorded using the Norwegian Version of the Lawton IADL scale, which is a valid and reliable measure of a person's self-reported ability to perform complex activities of daily living [61].

Physical activity is measured using the “Walking habits questionnaire”, a valid questionnaire for walking habits and physical activity for frailer older people [62]. This questionnaire assesses general behaviour of walking, regarding how often and for how long. The following questions are asked: “Do you take a daily walk?” (yes/no) or “If you do not take a daily walk how many times per week do you take a walk?” (never/almost never/1-2 days/3-4 days/ almost daily) and “How long does you walk generally last? (0-15 mins/15-30mins/30-60mins/ 1h-2h/>2h)”. Walking time in minutes per week is calculated by taking the lowest level of days multiplied by lowest level of minutes for each response alternative [62].

Nutritional status is measured using the Mini Nutritional Assessment (MNA- elderly, Société des Produits Nestlé, S.A., Vevey, Switzerland) form. The first screening part of six questions is used which includes measurement of weight and height for calculation of BMI [63-65].

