Falls efficacy is assessed using the Falls Efficacy Scale International (FES-I). This scale has shown good reliability and validity assessing concerns about falling in older adults, and is recommended for clinical trials and practise [66, 67]. It is a self-reported questionnaire, containing 16 items on different activities of daily living. Level of concern is measured on a four-point scale ranging from 1, which is not at all concerned, to 4 which is very concerned [68].

Adherence to the programme is documented through an activity diary completed by the participants and a form checked by the physiotherapists during home visits and calls. Additionally, the participants have a falls calendar where they report adverse events. Adverse events are registered in the following four categories: falls, cardiovascular events, musculoskeletal injuries and health care utilization and will be documented as “due to the intervention” or “not due to the intervention” [69].

Sample size estimation

The sample size is estimated from the primary outcome, HRQOL (SF-36). A treatment difference of 10 points between the two groups in one of the domains in SF-36 is regarded to be of statistical and clinical significance. The associated standard deviation is assumed to be around 20 points. This implies a moderate effect size [70], which can be expected as previous OEP studies have shown substantial effects on physical outcomes [45]. Moreover, a similar Norwegian study, which included older adults performing exercise following discharge from hospital, estimated the required sample size identically [71]. Given a power of 80% and level $\alpha=0.05$, we aim at including 150 participants, allowing for a 15-20% dropout, to detect a difference of 10 points between groups (see Figure 1).

Statistical procedures

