Statistical analysis is performed using SPSS or a similar statistical package. Descriptive data are reported for variables of interest. The data will be analysed following the intention to treat principle [72]. Prospective differences in primary and secondary outcomes and baseline characteristics between the intervention group and the control group will be assessed by t-tests for continuous and normal distributed variables and with non-parametric tests for categorical variables. Multiple linear regression modelling are used to control for confounding of between-group differences [73]. Hypotheses about mediating factors are tested through correlations, multiple regressions and bootstrapping methods exploring the correlations and explained variance of the chosen mediating factors and the changes in QOL [74]. Bootstrapping is a non-parametric method and is considered favourable with dichotomous variables (group 1 and 2) and small samples ($n < 250$) [74].

Discussion

The main purpose of the study is to evaluate the impact of OEP on HRQOL in older adults receiving home help services. We anticipate that the intervention described in this protocol will have a positive impact on the HRQOL. The tailored intervention will have a potential to promote evidence-based decision-making and empower older people receiving home help services to remain to a greater extent in charge of their own lives. We rely on a systematic approach, which corresponds with the guidance on developing and evaluating RCTs [75]. Only a few studies have included HRQOL when measuring the effect of a falls prevention programme, and most of these studies include it as a secondary outcome [21, 76]. Outcomes examining HRQOL are selected based on literature identifying a standard set of measurements in falls prevention programmes [77, 78]. SF-36 is chosen due to its good validity, reliability and responsiveness when assessing older adults [79]. This outcome is detailed and broad, but it might be putting a burden on the participants due to its length and sensitive questions. Nevertheless, estimating HRQOL is important to determine whether the effect of a falls prevention programme is significant enough to achieve clinical relevant changes and thus to justify the implementation.

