Eligibility criteria	10	Inclusion and exclusion criteria for participants. If applicable, eligibility criteria for study centres and individuals who will perform the interventions (eg, surgeons, psychotherapists)	6
Interventions	11a	Interventions for each group with sufficient detail to allow replication, including how and when they will be administered	7-8
	11b	Criteria for discontinuing or modifying allocated interventions for a given trial participant (eg, drug dose change in response to harms, participant request, or improving/worsening disease)	
	11c	Strategies to improve adherence to intervention protocols, and any procedures for monitoring adherence (eg, drug tablet return, laboratory tests)	8, 10
	11d	Relevant concomitant care and interventions that are permitted or prohibited during the trial	6
Outcomes	12	Primary, secondary, and other outcomes, including the specific measurement variable (eg, systolic blood pressure), analysis metric (eg, change from baseline, final value, time to event), method of aggregation (eg, median, proportion), and time point for each outcome. Explanation of the clinical relevance of chosen efficacy and harm outcomes is strongly recommended	8-10
Participant timeline	13	Time schedule of enrolment, interventions (including any run-ins and washouts), assessments, and visits for participants. A schematic diagram is highly recommended (see Figure)	6-7, 9, Figure 1

Sample size	14	Estimated number of participants needed to achieve study objectives and how it was determined, including clinical and statistical assumptions supporting any sample size calculations	10
Recruitment	15	Strategies for achieving adequate participant enrolment to reach target sample size	6

Methods: Assignment of interventions (for controlled trials)

Allocation:

Sequence generation	16a	Method of generating the allocation sequence (eg, computer-generated random numbers), and list of any factors for stratification. To reduce predictability of a random sequence, details of any planned restriction (eg, blocking) should be provided in a separate document that is unavailable to those who enrol participants or assign interventions	6-7
Allocation concealment mechanism	16b	Mechanism of implementing the allocation sequence (eg, central telephone; sequentially numbered, opaque, sealed envelopes), describing any steps to conceal the sequence until interventions are assigned	6-7,

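### The between-group test is a t-test with no pre-specified baseline adjustment and no stated metric; a linear model on the baseline score would gain about 3 to 19 points of power, depending on the metric and an assumed correlation of 0.3 to 0.7

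*Combined protocol and SAP*

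**What the plan says.** The Statistical procedures section gives the between-group analysis in two sentences. The first covers "Prospective differences in primary and secondary outcomes and baseline characteristics between the intervention group and the control group", which "will be assessed by t-tests for continuous and normal distributed variables and with non-parametric tests for categorical variables". The second adds: "Multiple linear regression modelling are used to control for confounding of between-group differences". No covariate is listed, the baseline value of the outcome is not mentioned, and neither analysis is named as the main one.

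The Outcome measures section establishes that baseline scores will exist and come before allocation: "Following recruitment participants are assessed before they are randomised", and "Primary and secondary outcome measures will be performed at baseline, at three months and at six months".

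The Sample size estimation section uses a 10-point difference on one SF-36 domain, 80% power, a 5% level and 150 participants with 15–20% dropout. On variability it says: "The associated standard deviation is assumed to be around 20 points". It does not say whether this is the SD of a score at one visit or of a change.

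Item 12 of the SPIRIT checklist, which asks for the analysis metric of each outcome, is marked as addressed on pages 8–10. The Methods text states no metric for the between-group test.

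**The concern.** Two things are left open, and both affect precision.

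First, the metric. Prospective differences could mean follow-up scores or changes from baseline, and the two t-tests can differ widely in power. Which is weaker depends on the correlation r between baseline and follow-up scores. With equal SDs at both visits, the change-score test is weaker when r is below 0.5 and the follow-up-score test is weaker when r is above 0.5. Choosing either one is a bet on a quantity the documents do not give.

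Second, the baseline score is the natural covariate. It is collected anyway and cannot be affected by allocation. A linear model that includes it does at least as well as the better t-test (apart from one degree of freedom), so r need not be guessed. The plan's regression might include it, but nothing commits the plan to that. An unranked pair of analyses with unnamed covariates also leaves room to choose after the data are seen.

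The same sentence applies significance tests to baseline characteristics. In a randomised comparison any such difference arises by chance, so those tests tell the reader nothing.

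**Working it through.** **Inputs from the protocol.** Difference 10; SD 20; 5% level; 80% power; 1:1 allocation; 150 randomised; 15–20% dropout.

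**Assumptions.** Two-sided test (sidedness is not stated); equal SD at baseline and follow-up; r = 0.3, 0.5 or 0.7.

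**The plan's own figure.** A two-sample comparison of 10 points with SD 20 needs 63 per arm by the normal approximation, or 64 by the exact t. Allowing for 15% dropout, 126/0.85 = 149 and 128/0.85 = 151, so 150 is reproduced. At 20% dropout the requirement would be 126/0.80 = 158 to 128/0.80 = 160.

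**Completers per arm.** 150 × 0.80 / 2 = 60; 150 × 0.85 / 2 = 63.75, taken as 64.

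**SD relevant to each analysis, taking 20 as the SD at one visit:**
- Follow-up score: 20
- Change score: 20√(2(1 − r)) = 23.7 / 20.0 / 15.5
- ANCOVA residual: 20√(1 − r²) = 19.1 / 17.3 / 14.3

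Since 1 − r² = (1 − r)(1 + r), the ANCOVA residual SD is never larger than either of the others.

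**Power.** Noncentral t with noncentrality 10 / (SD × √(2/n)). Degrees of freedom are 2n − 2 for the t-tests and 2n − 3 for ANCOVA. For the follow-up test at n = 60 the noncentrality is 10 / (20 × √(2/60)) = 10/3.65 = 2.74.

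| 60 per arm | r = 0.3 | r = 0.5 | r = 0.7 |
|---|---|---|---|
| Follow-up-score t-test | 77.5% | 77.5% | 77.5% |
| Change-score t-test | 63.1% | 77.5% | 93.9% |
| ANCOVA | 81.3% | 88.0% | 96.7% |
| Gain over follow-up test (points) | 3.7 | 10.5 | 19.2 |
| Gain over change test (points) | 18.1 | 10.5 | 2.8 |
| 95% CI half-width: follow-up / change / ANCOVA | 7.2 / 8.6 / 6.9 | 7.2 / 7.2 / 6.3 | 7.2 / 5.6 / 5.2 |

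(Gains are taken before rounding the powers.)

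**At 64 per arm (15% dropout).** Follow-up test 80.1%; change test 66.0 / 80.1 / 95.2%; ANCOVA 83.7 / 90.0 / 97.6%. Gains are 3.6 / 9.8 / 17.4 points over the follow-up test and 17.7 / 9.8 / 2.4 over the change test.

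**If SD 20 is the SD of change.** The ANCOVA residual SD is then 20√((1 + r)/2) = 16.1 / 17.3 / 18.4. At 60 per arm a change-score t-test has 77.5% and ANCOVA has 92.1 / 88.0 / 83.8%, a gain of 14.5 / 10.5 / 6.3 points.

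**Simulation check (20,000 trials, 60 per arm, SD 20 at one visit).** Follow-up test 78.0 / 77.1 / 77.9%; change test 63.4 / 77.2 / 93.8%; ANCOVA 81.6 / 87.6 / 96.6%. These agree with the exact figures.

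**The case against.** The strongest reply is that an adjusted linear model is already planned. If the baseline score is entered in it and that model is read as the main result, no power is lost. This is fair as far as it goes: the gains above are what is forgone when the t-test decides, or when the regression omits baseline. But the plan promises neither the covariate nor the ranking, and an analyst who follows the t-test sentence as written gets the less precise result.

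A second reply is that nothing is wrong with the t-test. It is valid under randomisation and has about 78–80% power on the plan's inputs if follow-up scores are tested. That stands, and it is why this is a recommendation on efficiency and no more.

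A third is that the range rests on an undocumented r and spans two metrics, with the large gains at opposite ends: low r for change scores, high r for follow-up scores. No single reading of the plan spans the whole range. This also stands, and the range should be read with its conditions. It is not an overstatement, though. If 20 is the SD of change but follow-up scores are tested, the follow-up SD is 20/√(2(1 − r)) = 16.9 / 20.0 / 25.8. At 60 per arm the test then has 89.5 / 77.5 / 55.7% power, and ANCOVA gains 2.5 / 10.5 / 28.1 points, which reaches beyond the headline figure. That case mixes metrics, so it is not used there.

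**Conclusion.** The concern holds. The plan's stated test neither fixes the metric nor uses a prognostic covariate that is already collected. With 60 completers per arm, a 10-point difference, SD 20 at each visit and r between 0.3 and 0.7, ANCOVA has 2.8 to 19.2 points more power than the t-test it would replace. At r = 0.5 the gain is 10.5 points against either metric. With 64 per arm the range is 2.4 to 17.7.

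The omission is clear from the text. The size of the gain depends on an assumed correlation and on how the SD is read, but ANCOVA had the higher power in every case computed. With 20% dropout it also brings power above the planned 80% at each r shown, where the follow-up-score t-test stands at 77.5%. The change should be made; the trial's validity does not depend on it.

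**What to change.** Make the main between-group analysis of each SF-36 scale a linear model of the follow-up score on arm and the baseline value of that scale. Fit it at three and at six months, and report the adjusted mean difference with its 95% CI. Apply it to whichever scale and time point is named primary.

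Use the same model for continuous secondary scales such as the Berg Balance Scale, gait speed, sit-to-stand and FES-I. Keep a non-parametric or ordinal method for categorical or coarsely banded outcomes. Walking time is one of these, because its minutes are "calculated by taking the lowest level of days multiplied by lowest level of minutes".

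List any further covariates in advance. Keep the unadjusted t-test as supportive, and describe baseline characteristics without significance tests.

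The cost is wording in the analysis plan. The data are already collected before randomisation, and SPSS, the package the plan names, fits the model. Each covariate uses one degree of freedom, and linearity and residuals need the usual checks. The change does not settle which of the eight scales or two follow-up times is primary; that needs its own decision.

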88. World Health Organization: **WHO Global Report on Falls Prevention in Older Age.** Geneva, 2007.

[figure not shown]

Figure 1: Planned flow of participants in the study.

SPIRIT 2013 Checklist: Recommended items to address in a clinical trial protocol and related documents*

Section/item	Item No	Description	Addressed on page number
Administrative information			
Title	1	Descriptive title identifying the study design, population, interventions, and, if applicable, trial acronym	1, 2
Trial registration	2a	Trial identifier and registry name. If not yet registered, name of intended registry	2
	2b	All items from the World Health Organization Trial Registration Data Set	2
Protocol version	3	Date and version identifier	
Funding	4	Sources and types of financial, material, and other support	14
Roles and responsibilities	5a	Names, affiliations, and roles of protocol contributors	1, 14
	5b	Name and contact information for the trial sponsor	14
	5c	Role of study sponsor and funders, if any, in study design; collection, management, analysis, and interpretation of data; writing of the report; and the decision to submit the report for publication, including whether they will have ultimate authority over any of these activities	14
	5d	Composition, roles, and responsibilities of the coordinating centre, steering committee, endpoint adjudication committee, data management team, and other individuals or groups overseeing the trial, if applicable (see Item 21a for data monitoring committee)	14

Introduction

Background and rationale	6a	Description of research question and justification for undertaking the trial, including summary of relevant studies (published and unpublished) examining benefits and harms for each intervention	3-5
	6b	Explanation for choice of comparators	6
Objectives	7	Specific objectives or hypotheses	5, 10-11
Trial design	8	Description of trial design including type of trial (eg, parallel group, crossover, factorial, single group), allocation ratio, and framework (eg, superiority, equivalence, noninferiority, exploratory)	6
Methods: Participants, interventions, and outcomes			
Study setting	9	Description of study settings (eg, community clinic, academic hospital) and list of countries where data will be collected. Reference to where list of study sites can be obtained	6
Eligibility criteria	10	Inclusion and exclusion criteria for participants. If applicable, eligibility criteria for study centres and individuals who will perform the interventions (eg, surgeons, psychotherapists)	6
Interventions	11a	Interventions for each group with sufficient detail to allow replication, including how and when they will be administered	7-8
	11b	Criteria for discontinuing or modifying allocated interventions for a given trial participant (eg, drug dose change in response to harms, participant request, or improving/worsening disease)	
	11c	Strategies to improve adherence to intervention protocols, and any procedures for monitoring adherence (eg, drug tablet return, laboratory tests)	8, 10
	11d	Relevant concomitant care and interventions that are permitted or prohibited during the trial	6
Outcomes	12	Primary, secondary, and other outcomes, including the specific measurement variable (eg, systolic blood pressure), analysis metric (eg, change from baseline, final value, time to event), method of aggregation (eg, median, proportion), and time point for each outcome. Explanation of the clinical relevance of chosen efficacy and harm outcomes is strongly recommended	8-10
Participant timeline	13	Time schedule of enrolment, interventions (including any run-ins and washouts), assessments, and visits for participants. A schematic diagram is highly recommended (see Figure)	6-7, 9, Figure 1

Sample size	14	Estimated number of participants needed to achieve study objectives and how it was determined, including clinical and statistical assumptions supporting any sample size calculations	10
Recruitment	15	Strategies for achieving adequate participant enrolment to reach target sample size	6

Methods: Assignment of interventions (for controlled trials)

Allocation:

Sequence generation	16a	Method of generating the allocation sequence (eg, computer-generated random numbers), and list of any factors for stratification. To reduce predictability of a random sequence, details of any planned restriction (eg, blocking) should be provided in a separate document that is unavailable to those who enrol participants or assign interventions	6-7
Allocation concealment mechanism	16b	Mechanism of implementing the allocation sequence (eg, central telephone; sequentially numbered, opaque, sealed envelopes), describing any steps to conceal the sequence until interventions are assigned	6-7,
Implementation	16c	Who will generate the allocation sequence, who will enrol participants, and who will assign participants to interventions	6
Blinding (masking)	17a	Who will be blinded after assignment to interventions (eg, trial participants, care providers, outcome assessors, data analysts), and how	7-9
	17b	If blinded, circumstances under which unblinding is permissible, and procedure for revealing a participant's allocated intervention during the trial	6

Methods: Data collection, management, and analysis

Data collection methods	18a	Plans for assessment and collection of outcome, baseline, and other trial data, including any related processes to promote data quality (eg, duplicate measurements, training of assessors) and a description of study instruments (eg, questionnaires, laboratory tests) along with their reliability and validity, if known. Reference to where data collection forms can be found, if not in the protocol	8-10
	18b	Plans to promote participant retention and complete follow-up, including list of any outcome data to be collected for participants who discontinue or deviate from intervention protocols	7

Data management	19	Plans for data entry, coding, security, and storage, including any related processes to promote data quality (eg, double data entry; range checks for data values). Reference to where details of data management procedures can be found, if not in the protocol	Included in ethical approval, p.14
Statistical methods	20a	Statistical methods for analysing primary and secondary outcomes. Reference to where other details of the statistical analysis plan can be found, if not in the protocol	10
	20b	Methods for any additional analyses (eg, subgroup and adjusted analyses)	10
	20c	Definition of analysis population relating to protocol non-adherence (eg, as randomised analysis), and any statistical methods to handle missing data (eg, multiple imputation)	6-7

Methods: Monitoring

Data monitoring	21a	Composition of data monitoring committee (DMC); summary of its role and reporting structure; statement of whether it is independent from the sponsor and competing interests; and reference to where further details about its charter can be found, if not in the protocol. Alternatively, an explanation of why a DMC is not needed	14
	21b	Description of any interim analyses and stopping guidelines, including who will have access to these interim results and make the final decision to terminate the trial	10, 14
Harms	22	Plans for collecting, assessing, reporting, and managing solicited and spontaneously reported adverse events and other unintended effects of trial interventions or trial conduct	10
Auditing	23	Frequency and procedures for auditing trial conduct, if any, and whether the process will be independent from investigators and the sponsor	NA

Ethics and dissemination

Research ethics approval	24	Plans for seeking research ethics committee/institutional review board (REC/IRB) approval	14
Protocol amendments	25	Plans for communicating important protocol modifications (eg, changes to eligibility criteria, outcomes, analyses) to relevant parties (eg, investigators, REC/IRBs, trial participants, trial registries, journals, regulators)	14

Consent or assent	26a	Who will obtain informed consent or assent from potential trial participants or authorised surrogates, and how (see Item 32)	6, 14
	26b	Additional consent provisions for collection and use of participant data and biological specimens in ancillary studies, if applicable	NA
Confidentiality	27	How personal information about potential and enrolled participants will be collected, shared, and maintained in order to protect confidentiality before, during, and after the trial	Included in ethical approval, p.14
Declaration of interests	28	Financial and other competing interests for principal investigators for the overall trial and each study site	14
Access to data	29	Statement of who will have access to the final trial dataset, and disclosure of contractual agreements that limit such access for investigators	14
Ancillary and post-trial care	30	Provisions, if any, for ancillary and post-trial care, and for compensation to those who suffer harm from trial participation	8
Dissemination policy	31a	Plans for investigators and sponsor to communicate trial results to participants, healthcare professionals, the public, and other relevant groups (eg, via publication, reporting in results databases, or other data sharing arrangements), including any publication restrictions	14
	31b	Authorship eligibility guidelines and any intended use of professional writers	
	31c	Plans, if any, for granting public access to the full protocol, participant-level dataset, and statistical code	14
Appendices			
Informed consent materials	32	Model consent form and other related documentation given to participants and authorised surrogates	Included in ethical approval
Biological specimens	33	Plans for collection, laboratory evaluation, and storage of biological specimens for genetic or molecular analysis in the current trial and for future use in ancillary studies, if applicable	

*It is strongly recommended that this checklist be read in conjunction with the SPIRIT 2013 Explanation & Elaboration for important clarification on the items. Amendments to the protocol should be tracked and dated. The SPIRIT checklist is copyrighted by the SPIRIT Group under the Creative Commons [“Attribution-NonCommercial-NoDerivs 3.0 Unported”](#) license.
